2.1.1 General definitions

Investigational treatment will be LTP001.

Date of first administration of study treatment (Day 1) will be defined as the date of the first actual administration of LTP001.

Date of last administration of study treatment will be defined as the date of the last actual administration of LTP001.

Two *Baselines* will be defined as the following:

Baseline of the Parent study: the Day 1 assessment of study LTP001A12201. If this datum is not available, the last pre-dosing assessment will be considered.

Baseline of the Extension study: Week 25 visit from LTP001A12201. If this datum is not available, the last pre-dosing assessment for this study (LTP001A12201E1) will be considered. *Study day* will be defined as the number of days since the date of first dose of study treatment (LTP001 or placebo). The date of first dose of study treatment will be defined as *Day 1* and the day prior to first dose of will be defined as *Day -1*. Therefore, for a particular date, study day will be calculated as follows:

for dates on or after the date of first dose of study treatment,

Study day = Assessment date – Date of first dose administration + 1

The on-treatment period lasts from the date of first administration of study treatment to the End of Study (EOS) visit or the date of last randomized dose if EOS visit is not available. The EOS visit is a follow-up visit that is approximately 30 days after the date of the last actual administration of investigational treatment. For participants who will be enrolled into the open label extension (OLE) study, their EOS visits will be skipped.

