2.5.1 Primary endpoint(s)

Safety assessment will include AEs, SAEs, vital signs, ECGs, and safety laboratory measurements.

Adverse events (AEs)

All Adverse events in the extension study will be summarized and listed. Also, all study emergent AEs in both the parent study and extension study will be summarized.

Consistent with the parent study CLTP001A12201 definitions, AEs starting after the first dose of study medication or events present prior to start of treatment but increased in severity based on preferred term will be classified as a treatment emergent AE. The definition of the on treatment period is defined in [Section 2.1.1](#). The following treatment emergent adverse events summaries will be produced:

- by primary system organ class and preferred term
- by primary system organ class, preferred term and maximum severity
- by Standardized MedDRA Query (SMQ) and preferred term.

The number and percentage of participants with adverse events will be summarized.

Separate summaries will be provided for study medication related adverse events, serious adverse events, other significant adverse events leading to discontinuation. In case of sparse events in any of these categories occur, only a listing will be provided if deemed adequate.

The number and percentage of deaths, including on-treatment and post-treatment deaths, will be summarized and listed.

Adverse events of special interest/grouping of AEs is not defined in this study.

Vital signs

Vital signs will include the collection of otic or oral body temperature (recorded in °C), blood pressure (BP) and pulse measurements.

All vital signs data will be listed by participant, and visit/time and if ranges are available, abnormalities will be flagged. Summary statistics (including N, mean, SD, minimum, median, maximum) of vital signs and changes from baseline will be provided by visit/time. Graphical presentations (e.g., boxplots) of vital signs will be provided by visit/time.

Electrocardiogram (ECG)

All ECG data, including PR, QRS, QT, QTcF and RR, will be listed by participant and visit/time, and abnormalities will be flagged. Summary statistics and graphical presentations (e.g. boxplots) will be provided by visit/time.

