Categorical Analysis of QTcF (Fridericia's formula) interval data based on the number of participants meeting or exceeding predefined limits in terms of absolute QT or QTc intervals or changes from baseline will be presented. The number and percentage of participants with clinical notable QTcF will be summarized by visit. A listing of these participants will be provided. The clinical notable criteria for QTcF (Fridericia's formula) are indicated in [Table 2-2](#).

Table 2-2 Clinical notable criteria for QTcF (Fridericia's formula)

ECG parameter (unit)	Clinically notable range
Notable value considering newly occurring or worsening cases	
QTcF (msec)	> 500
QTcF (msec)	> 480 if normal at baseline
QTcF (msec)	> 450
Notable change from baseline	
QTcF (msec)	> 60
QTcF (msec)	> 30

Laboratory data

All laboratory data will be listed by participant and visit/time and if normal ranges are available, abnormalities will be flagged. A separate listing is provided presenting all parameters in a subject with any abnormal values. Descriptive statistics (N, mean, SD, minimum, median, and maximum) summarizing continuous laboratory results of clinical chemistry, hematology, urinalysis, and changes from baseline by visit/time will be provided. Graphical presentations (e.g., boxplots) will be provided by visit/time.

Shift tables using the low/normal/high/ (low and high) classification will be used to compare baseline to the worst on-treatment value.

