5.3 Laboratory parameters derivations

The following table shows the direction of interest when analyzing worst case values in form of maximum and/or minimum post-baseline values. If the direction of interest is given as "High" the maximum value will be calculated and used as worst value, if the direction is given as "Low" the minimum value will be taken, and if it is given as "Low and high", both the minimum value and the maximum value will be calculated and presented in summary tables.

Table 5-1 Directions of interest for worst case value for laboratory parameters

Laboratory Parameter	Direction of interest for worst case value
A. Hematology	
Hemoglobin	Low
Hematocrit	Low
Erythrocytes	Low
WBC	Low and high
Basophils	High
Eosinophils	High
Lymphocytes	Low and high
Monocytes	High
Neutrophils	Low and high
Platelets	Low and high

B. Chemistry	
Albumin	Low
Alkaline Phosphatase	High
ALT/SGPT	High
AST/SGOT	High
Bilirubin Total	High
Blood Urea Nitrogen (BUN)	High
Creatinine	High
Gamma GT	High

Potassium	Low and high
Magnesium	Low and high
Calcium	Low and high
LDH	High
Phosphorus	Low and high
Sodium	Low and high
CRP	High
Fibrinogen	High
HbA1c	Low and high

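### The SAP's fallback end date for the on-treatment period does not exist in this non-randomized extension, and it decides how deaths before the 30-day contact are classified

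*SAP*

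**What the plan says.** **Start.** SAP 2.1.1 says: "Date of first administration of study treatment (Day 1) will be defined as the date of the first actual administration of LTP001". A few lines later it counts study day as "the number of days since the date of first dose of study treatment (LTP001 or placebo"). It also uses a Day 1 label for the parent baseline: "the Day 1 assessment of study LTP001A12201".

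**End.** The on-treatment period runs to the EOS visit, described as a follow-up about 30 days after the last LTP001 dose, or to "the date of last randomized dose if EOS visit is not available". SAP 2.1.1 then adds: "For participants who will be enrolled into the open label extension (OLE) study, their EOS visits will be skipped".

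**Use.** SAP 2.5.1 refers back to this period for adverse events and states: "The number and percentage of deaths, including on-treatment and post-treatment deaths, will be summarized and listed". The laboratory shift tables "will be used to compare baseline to the worst on-treatment value".

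**Design facts.** SAP 1.1 calls the study non-randomized, and protocol 6.3.1 marks randomization as not applicable. Protocol Table 1-2 places the Post Study Safety Contact 30 days after last treatment, with a window of minus 0 to plus 7 days. Protocol 8.6.1 continues AE monitoring for at least 30 days after the last dose, and 8.6.3 requires SAE reporting over the same 30 days.

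**TTCW.** SAP 2.6.1.1 lists the component events but gives no start date. It censors event-free participants at the end of a time at risk that it does not define. Protocol 9.4.1 supplies neither.

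**The concern.** The fallback names a kind of dose that this study does not give. It is also the rule that applies to the participants for whom the on-treatment boundary matters most. A person who has died cannot take part in the follow-up contact, so any death between the last dose and that contact is classified by the fallback alone. If the fallback is shorter than the main rule, deaths and survivors are judged on different windows.

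The sentence about skipped EOS visits adds to the problem. Read literally, it covers everyone in this study and would send all participants to the fallback.

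At stake is the split of deaths into on-treatment and post-treatment, a summary under the primary objective.

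**Working it through.** The plan states no figure on this point to reproduce. The check sets the rules side by side and counts days.

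**Inputs.** L is the date of the last LTP001 dose in the extension. The contact takes place at L + 30 to L + 37 days (protocol Table 1-2). AE monitoring runs to at least L + 30 (protocol 8.6.1). Dosing is once daily (protocol 4.3).

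**Step 1: end of the on-treatment period.**

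| Situation | End date | Deaths before the contact that count as on-treatment |
|---|---|---|
| EOS contact took place | L + 30 to L + 37 | Not applicable: the participant was alive at the contact |
| No EOS contact; fallback taken literally | A parent-study date, if any | None |
| No EOS contact; fallback read as the last extension dose | L | Only those dated on day L |
| Fixed rule for everyone | L + 30 | All those up to L + 30 |

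**Step 2: an example.** Suppose the last dose is on Day 358, the scheduled Week 52 day.
- A participant who reaches the contact is on-treatment to 358 + 30 = Day 388 at the earliest and 358 + 37 = Day 395 at the latest.
- A participant who dies on Day 368, 10 days after the last dose, has no contact. Under the last-dose reading the period ended on Day 358, so the death is post-treatment.
- Day 368 is on-treatment for the first participant and post-treatment for the second, although both had the same last dose.

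**Step 3: deaths during ongoing treatment.** With once-daily dosing, a participant who dies before taking that day's dose last took LTP001 the day before. The death falls on L + 1 and, under the last-dose reading, is post-treatment.

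**Step 4: what the main rule adds.** The extra 30 to 37 days are given only when the contact took place. No death can fall in them, by construction. The on-treatment death count is then limited to deaths dated on day L, however many occur in the following 30 days.

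**Step 5: the skipped-EOS sentence taken literally.** Everyone goes to the fallback. The windows then agree between participants, but they end at L and leave out the 30 days over which AEs are still monitored. If the fallback is also taken literally, they contain no extension treatment at all.

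**Step 6: laboratory shift tables.** Table 1-2 schedules no laboratory test after the EOT visit, so the end date could affect only unscheduled samples. SAP 5.3 also takes the worst value "when analyzing worst case values in form of maximum and/or minimum post-baseline values", which limits the influence of the start date to comparisons with the parent baseline.

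**The case against.** **The wording is a slip that any programmer would repair.** SAP 2.1.1 defines the last administration as the last actual LTP001 dose, and that is the natural substitute. This is fair, but it is the repair that produces the unequal windows in Steps 2 to 4. Correcting one word does not settle whether the 30 days are added when there is no contact.

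**Deaths are listed individually.** With about 40 participants, a reader could check each one. That stands and limits the harm. The summarized count would still be wrong under a rule written in advance.

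**The skipped-EOS sentence looks forward and suits the parent study's own EOS visit.** That is probably its origin, although the parent SAP is not available to confirm it. It still does not belong in a definition for this study, whose participants have their own contact.

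**Stronger readings that a reader might infer, and why the documents do not support them:**
- *Two conflicting Day 1 dates corrupt the visit analyses.* For doses given in this study the two sentences give the same date, because only LTP001 is given. The visit days in SAP 2.6.1.1 (for example 176 and 358) confirm the extension clock. No SAP rule assigns visits by study day. The parent Day 1 is labeled as such. Any figure for the gap between the two clocks would need a parent visit calendar that these documents do not give.
- *The laboratory shift tables are materially affected.* Step 6 shows that they barely are.
- *The TTCW hazard ratio is biased.* That would need time counted from each person's first-ever LTP001 dose without delayed entry. The SAP does not state that clock. The Cox model is also conditional on an adequate number of events.

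**Conclusion.** The end rule is wrong as written and should be corrected before database lock. Even on its most favorable reading, every death after the last-dose day and before the contact is post-treatment, while a participant who reaches the contact is on-treatment for 30 to 37 days longer. The number of deaths affected cannot be predicted, because the plan gives no expected mortality. It could be zero.

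The conclusion rests on two assumptions: that EOS means this study's Post Study Safety Contact, and that the fallback means the last extension dose. Taken literally, the fallback counts no extension death without an EOS contact as on-treatment.

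The other points are smaller. The placebo wording in the study-day definition is redundant and should be tidied. The missing TTCW origin and undefined time at risk are gaps in detail, not a demonstrated bias. The choice of origin still matters for Kaplan-Meier as well as Cox. Counting from parent Day 1 would include a stretch that every entrant had to complete in order to be eligible, so delayed entry would be needed for both. The study is descriptive, so no test, error rate or power figure changes.

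**What to change.** **Main change (SAP 2.1.1).** Define the on-treatment period for every participant as the first LTP001 dose in the extension to the last LTP001 dose in the extension plus 30 days, whether or not an EOS contact took place. Delete the reference to a randomized dose and the sentence about skipped EOS visits.

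**In the same edit.** Remove placebo from the study-day definition, and give the parent and extension first-dose dates separate names.

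**TTCW (SAP 2.6.1.1).** State extension Day 1 as the origin, define the end of the time at risk, and say whether events in the parent period count. If parent Day 1 is preferred, specify delayed entry at extension Day 1 for both Kaplan-Meier and Cox.

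**Cost.** SAP wording and one date derivation, with no new data.

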Period	Baseline		Extension Treatment Up To Month 12							
Visit Name	Transition Period		Treatment						EOT	Post Study Safety Contact
Visit Numbers ¹	1 ²	100 ²	110		120		130	140	150	
Days	-14 to -1	1	29 ±7	57 ±10	85 ±10	113 ±10	176 ±10	267 ±10	358 ±10	Last treatment +30 -0 +7
Weeks	-2 to -1	1	5 ±1	9 ±2	13 ±2	17 ±2	26 ±2	39 ±2	52 ±2	57 -0 +1
Informed consent ^{3,4}	X									
Inclusion / Exclusion criteria	X									
Physical Examination			S	S ⁸	S	S ⁸	S	S	S	
Body Weight			X	X ⁸	X	X ⁸	X	X	X	
Body Temperature			X	X ⁸	X	X ⁸	X	X	X	
Blood Pressure and Pulse Rate			X	X ⁸	X	X ⁸	X	X	X	
Electrocardiogram (ECG)			X	X ⁸	X	X ⁸	X	X	X	
Dose administration ⁵	X	X	X ⁸	X	X ⁸	X	X	X	X	
Drug dispensation	X	X		X			X	X		
Collect study medication/perform drug accountability ⁵			X	X ⁸	X	X ⁸	X	X	X	
Urinalysis			X	X ⁸	X	X ⁸	X	X	X	
Pregnancy and assessments of fertility			S	S ⁸	S	S ⁸	S	S	S	
Hematology			X	X ⁸	X	X ⁸	X	X	X	
Clinical Chemistry			X	X ⁸	X	X ⁸	X	X	X	

Period	Baseline		Extension Treatment Up To Month 12								
Visit Name	Transition Period		Treatment						EOT	Post Study Safety Contact	
Visit Numbers ¹	1 ²	100 ²	110		120		130	140	150		
Days	-14 to -1	1	29 ±7	57 ±10	85 ±10	113 ±10	176 ±10	267 ±10	358 ±10	Last treatment +30 -0 +7	
Weeks	-2 to -1	1	5 ±1	9 ±2	13 ±2	17 ±2	26 ±2	39 ±2	52 ±2	57 -0 +1	
Coagulation Panel			X	X ⁸	X	X ⁸	X	X	X		
NT-proBNP				X		X		X	X		
emPHasis-10 and PAH-SYMPACT ⁶			X ⁷		X ⁷		X ⁷	X ⁷	X ⁷		
Right Heart Catheterization ⁴							X				
6-Minute Walk Test ⁴							X		X		
Echocardiogram ⁴							X		X		
Concomitant Medications/Adverse Events								X			
Study completion information									X		

Period	Baseline		Extension Treatment Up To Month 12							
Visit Name	Transition Period		Treatment					EOT	Post Study Safety Contact	
Visit Numbers ¹	1 ²	100 ²	110		120		130	140	150	
Days	-14 to -1	1	29 ±7	57 ±10	85 ±10	113 ±10	176 ±10	267 ±10	358 ±10	Last treatment +30 -0 +7
Weeks	-2 to -1	1	5 ±1	9 ±2	13 ±2	17 ±2	26 ±2	39 ±2	52 ±2	57 -0 +1
Safety Follow up Call			S		S					S

^X Assessment to be recorded in the clinical database or received electronically from a vendor

^S Assessment to be recorded in the source documentation only

¹ Visit structure given for internal programming purpose only

² Baseline and Day 1 can be on the same day or within a 14-day transition period

³ CCI

⁴ Assessment must be performed onsite. All other assessments may be performed at an off-site location.

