6.2.3 Instruction for prescribing and taking study treatment

LTP001 should be taken daily at approximately the same time each day **CCI**. On clinic visit days, the participant should take LTP001 during the clinic visit when instructed by the study staff. 6MWT and RHC assessment should be executed at approximately the same time after drug administration each time (tolerance window +/- 1 hour).

CCI

If vomiting occurs during the course of treatment, participants should not take the study treatment LTP001 again before the next scheduled dose.

Participants should be instructed not to make up missed doses. A missed dose is defined as a case when the full dose is not taken within 12 hours after the approximate time of the usual daily dosing. That day's dose should be omitted and the participant should continue treatment with the next scheduled dose.

The first day the participant is seen by an off-site health professional during the visit window, or the first day of a visit to the clinical site should be the dose recorded in the Dosage Form eCRF.

Novartis will provide the site with a participant study card to hand over to all study participants, which will state that the participant is participating in a clinical study and is receiving an investigational product. This participant study card will also include the contact information of the Study Doctor/Investigative Site. Designated study staff will instruct study participants to present this card to a medical care provider if they have any medical issues during the course of the study.

All kits of study treatment assigned by the IRT will be recorded in the IRT system.

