1.1 Study design

This is a non-randomized, open-label extension study over 52 weeks with LTP001 without a control treatment arm. Participants will be presented the opportunity to consider the extension study at the End of Treatment (EOT) visit (Week 25) of the parent study CLTP001A12201. The investigator will assess if the participant will continue by verifying that the participant has completed the parent study as planned. Moreover, at the EOT the investigator will determine the eligibility for the extension study (i.e. that none of the treatment discontinuation criteria were met and that the assessments at the EOT of the parent efficacy study were completed according to the parent protocol). The patient may directly continue into the extension study. If the patient does not directly continue in the extension study, the time between the end of treatment assessments in the parent study and the enrollment in the extension study i.e. during the transition period should be kept to a minimum (it should not exceed 14 days).

In case of a direct transition into the extension study after the end of treatment visit in the parent study, as not all assessment results will be available (e.g. the central lab assessments) at the same day the investigator will re-assess/reconfirm the eligibility as soon as outstanding results are received.

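### The SAP's fallback end date for the on-treatment period gives a participant who dies before the 30-day contact no post-dose window, so a death soon after dosing could be labelled post-treatment

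*SAP*

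**What the plan says.** SAP 2.1.1 starts the on-treatment period at the first administration of study treatment and runs it "to the End of Study (EOS) visit or the date of last randomized dose if EOS visit is not available". It places the EOS contact in time: "The EOS visit is a follow-up visit that is approximately 30 days after the date of the last actual administration of investigational treatment". The matching entry in the protocol's assessment schedule (Table 1-2) is the post-study safety contact, at "Last treatment +30 -0 +7" days.

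SAP 2.1.1 also defines a date that the fallback does not use: "Date of last administration of study treatment will be defined as the date of the last actual administration of LTP001".

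Under adverse events, SAP 2.5.1 points to Section 2.1.1 for the on-treatment period. Later in the same subsection it says: "The number and percentage of deaths, including on-treatment and post-treatment deaths, will be summarized and listed". Neither kind of death is defined separately.

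The protocol asks for AE monitoring for at least 30 days after the last dose (8.6.1) and for reporting of every SAE up to 30 days after the last administration (8.6.3).

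**The concern.** Long-term safety is the primary objective, and deaths are part of the primary safety output. Under this rule the outcome being classified shortens its own window. Dying before the contact removes the EOS date, and the period then falls back to a dose date with no days added.

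This is more than a corner case. Protocol 7.1 requires study treatment to stop for WHO Functional Class IV symptoms, for a need for transplantation or atrial septostomy, and (unless waived after discussion with the medical monitor) for severe or serious drug-related events. In such participants some gap between last dose and death is to be expected. A drug-related serious event that leads to discontinuation, with death three days later, would be post-treatment under the fallback. Yet the event and the death lie inside the window in which the protocol requires SAE reporting.

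The fallback also names a 'randomized' dose, although the SAP says of this study: "This is a non-randomized, open-label extension study over 52 weeks with LTP001 without a control treatment arm". A programmer has to guess which date is meant.

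**Working it through.** The plan states no figure to reproduce. The check applies the date rule to deaths at different times after the last dose.

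**Inputs**
- Normal end of period: EOS contact, c days after last dose, with c from 30 to 37 (SAP 2.1.1; Protocol Table 1-2).
- Fallback end: date of last dose, +0 days (SAP 2.1.1, read as the last LTP001 dose).
- SAE reporting window: 30 days after last dose (Protocol 8.6.3).
- Participants: about 40 (Protocol Section 5).

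**Rules**, with d = days from last dose to death:
- As written: the window ends at c if the contact takes place, otherwise at 0. A death before the contact is on-treatment only if d ≤ 0.
- With a 30-day rule: the window ends at min(d, 30). A death is on-treatment if d ≤ 30.

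| Death before the contact, days after last dose | As written | 30-day rule |
|---|---|---|
| 0 | on | on |
| 1, 2, 7, 14, 29 | post | on |
| 30, contact not yet made | post | on |
| 31 to 37, contact not yet made | post | post |

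So only deaths on days +1 to +30 change row. A participant who reaches the contact has 30 to 37 post-dose days; one who dies first has 0.

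**Size per death:** 1/40 = 2.5 percentage points leave one row and enter the other. Two deaths would be 2/40 = 5 points. The documents give no expected number of deaths, so no total is estimated.

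**Does other text rescue the rule?** The SAP has no other on-treatment definition, no fixed post-dose window, and no statement that the date of death stands in for EOS. In the AE date imputation rules (SAP 5.1.2), study end date and date of death are listed as separate items, so the SAP names death where it wants death used.

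**What else uses the period?** The laboratory shift tables in SAP 2.5.1 compare baseline with the worst on-treatment value. A participant who stops early is to complete the end-of-treatment visit as soon as possible (Protocol 1.3), which can fall after the last dose. If the later contact is missed, whether through death or loss to follow-up, laboratory values from that visit fall outside the period.

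**The case against.** The link to deaths is an inference. SAP 2.5.1 cites Section 2.1.1 beside the treatment-emergent AE definition, and the death sentence comes later without a citation. This stands. The text supports saying that such a death could be classed as post-treatment, not that it certainly would be. Equating the SAP's EOS visit with the protocol's post-study phone contact is also an inference, though the 30-day timing agrees.

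The consequence is limited. Total deaths are unchanged and every death is listed. The treatment-emergent AE sentence has a start boundary but no end boundary of its own, so the fatal event may still appear in the AE tables, and serious events have a separate summary. There is no comparator and no test on these data. With about 40 participants, a reader can check each listed death. All of this stands and sets the weight of the point. What remains is a stated rule that gives the wrong label, and a death table that may disagree with the AE tables.

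Three stronger readings are tempting, and the documents do not support them:
- A reader might take the last randomized dose to be the last dose in the parent study, so that no extension death before the contact is on-treatment. For participants on placebo in the parent study, the period would then end at or before the first LTP001 dose that starts it. That is not a workable reading; the phrase is better seen as carried over from the parent study.
- SAP 2.1.1 adds: "For participants who will be enrolled into the open label extension (OLE) study, their EOS visits will be skipped". Taken literally here, everyone would get the 0-day fallback. The sentence makes sense only for the parent study, and it supports the view that the paragraph was carried over.
- A reader might infer that deaths after day +30 are under-collected, because Protocol 8.6.3 then asks for SAE reports only when a causal link is suspected. That rule concerns reports to the sponsor's safety group. Death is also a component of time to clinical worsening, and Protocol 7.1 continues AE and SAE collection after treatment discontinuation. The documents do not show how complete later deaths will be.

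**Conclusion.** The point holds as a defect in the on-treatment definition. A participant who dies before the EOS contact has a 0-day post-dose window, against 30 to 37 days for one who reaches it. If that definition governs the death split, deaths on days +1 to +30 are labelled post-treatment although they lie within the protocol's SAE reporting window. Each such death moves 2.5 percentage points between rows.

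The conclusion rests on three assumptions: the fallback means the last LTP001 dose, the SAP's EOS visit is the protocol's post-study contact, and the SAP's only on-treatment definition applies to deaths. The error affects the on-/post-treatment split and any other output bounded by the period, not the number of deaths reported. It should be corrected before database lock, but it does not put the study's overall safety account at risk.

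**What to change.** In SAP 2.1.1, define one on-treatment period for all safety outputs (deaths, AEs and worst on-treatment laboratory values). It should run from the first extension dose of LTP001 to 30 days after the last actual LTP001 dose, or to death if earlier, whether or not the EOS contact took place. Delete the reference to a last randomized dose. In SAP 2.5.1, state that the death split uses this period, and list later deaths with days since last dose.

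A rule for deaths alone would not be enough. It could label a death on-treatment while the laboratory values or AEs leading to it kept the 0-day fallback.

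The cost is SAP wording before database lock. No protocol amendment, contact or new data item is needed, because the rule uses the dates of first and last LTP001 dose and the date of death. There are two small downsides. The on-treatment death count may rise, and events between day +31 and a late contact (up to day +37) would no longer be on-treatment.
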